There are also reported effects of WS for which safety implications are unclear. Several studies have reported increased testosterone levels in males taking WS,⁵²⁻⁵⁵ but not in females.^{16,53} Elevated DHEA-S levels have been observed in a study of 50 aging, overweight males, with no related side effects,⁵² and a case report of a female patient with X-linked heterozygous adrenoleukodystrophy taking WS. However, other clinical trials that included female participants have found either *decreased* levels of DHEA-S⁵³ or no effect on DHEA-S.⁵⁶ DHEA is a precursor

Study Title: Safety, tolerability, and pharmacokinetics of an oral *Withania somnifera* product in older adults

Principal Investigator: [name], ND, MS

IRB#: STUDY00026055

Version Date: 10.10.2024

to testosterone. Testosterone will be assessed at the beginning and end of each four-week study period. Potentially related side effects will be assessed with an adverse events questionnaire every two weeks. The risk of taking WS while pregnant or breast-feeding is unknown and therefore, it is recommended to avoid WS during pregnancy and breast-feeding.

The intervention used in this study, Shoden®, is commercially available and has been studied in randomized, double-blind, placebo-controlled clinical trials, where it has been well-tolerated with no significant adverse events reported.^{52,53,57} The doses of Shoden® being used in this study are 240 and 480 mg. In a previous clinical trial of 60 participants, 240 mg Shoden® once daily for 60 days was not associated with any significant adverse events or laboratory abnormalities.⁵³ The higher dose of 480 mg was studied in a recently completed study of Shoden®, where it was well-tolerated after a single administration in 16 participants.⁵⁸ We anticipate that 480 mg of Shoden® will also be safe and well-tolerated over four weeks, but will closely monitor participants for potential adverse events, as described in Section N.

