An unpublished clinical trial conducted in India of Shoden® (CTRI/2020/10/028397) evaluated the PK of three withanolides (withanolide A, withaferin A, and withanoside IV) in 16 healthy adults, aged 18-45 years. All three withanolides were detected by LC-MRM-MS in plasma (data provided by Arjuna LTD under a NDA).⁷⁹ This study was limited in scope due to the dose (480 mg), which was higher than that used in clinical trials involving Shoden®,^{52,53,57} the lack of older participants, and the limited range of withanolides targeted.

E.3. LC-MS detection of withanolides

As part of ongoing research at the BENFRA Center, [name] and the BSR/PKCore at OHSU have been developing LC-MS methods of detecting withanolides in mouse plasma, which will be optimized for human plasma and urine as part of the study. Figure 2 demonstrates good separation for several of the withanolides that will be analyzed in this study.

F. RESEARCH DESIGN AND METHODS

F.1. Study design

The proposed study is a randomized, double-blind, crossover trial evaluating (a) the PK of withanolides, from two doses of a commercially available WS root and leaf extract (Shoden®), (b) safety and tolerability of these doses and (c) the feasibility of remotely measuring sleep- and stress-related outcomes in older adults. Participants will be randomized to one of two dose sequence groups. There will be two 4-week study periods separated by a 2- to 4-week washout period. During each study period, participants will attend a 13-hour baseline PK study visit and return for 24- and 48-hour blood and urine collections. After the 48-hour visit, they will continue taking Shoden® at the administered dose (240 or 480 mg) for four weeks, at which time they will return for a follow-up visit. A flow chart of the study is provided in Figure 3.

Study Design Diagram

[figure not shown]

Figure 3. Study design. *Mini Mental State Examination (MMSE); #Geriatric Depression Scale (GDS); *Biometrics: weight, height, body mass index (BMI), age, blood pressure, pulse rate, temperature; *Lab measures: complete blood count (CBC), comprehensive metabolic panel (CMP), urinalysis, and TSH; * REDCap surveys delivered to and completed by participants in the week prior to each PK visit and 4-Week Follow-Up Visit. §Safety assessment at study visits includes safety labs (CBC, CMP, TSH, testosterone, UA), GDS-15, ECG, and AE questionnaire.

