After the consent form is signed the participant's health status will be evaluated using a biometric assessment (height, weight, and body mass index), vital signs (blood pressure, pulse rate, temperature, and respiration rate), a screening physical exam, a mood assessment (Geriatric Depression Scale-15), and cognitive assessment (Mini-Mental State Examination). A non-fasting plasma and urinary laboratory evaluation (complete blood count (CBC), comprehensive metabolic panel (CMP), thyroid-stimulating hormone (TSH), and urinalysis) will be performed and submitted to the OHSU clinical core laboratory to screen for abnormalities that could impact study results. Study staff will collect approximately three teaspoons (15 ml) of venous blood by peripheral venipuncture and the participant will collect 20 ml of urine via a clean-catch method for analysis. A screening electrocardiogram (ECG) will also be taken at the screening visit. The visit is expected to take 60 to 90 minutes.

The study clinician ([name]) will review screening and laboratory results with the candidate prior to participant enrollment. Participants will be contacted by phone and told whether they qualify for the study or not. Participants who meet all final eligibility criteria will be invited to participate in the intervention stage of the study. The OHSU research pharmacy will randomize

each participant into one of two dose sequence groups. Any participant with abnormal health screening or laboratory evaluation will be directed to their primary care physician for treatment and excluded from the study. In the event that a participant does not qualify for the study, their data will be destroyed at the end of the study.

I.4. PK Visits 1 and 2

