Tolerability and safety: Participants' weight, height, body mass index, age, blood pressure, temperature, respiration rate, and pulse rate will be recorded at each study visit to monitor for adverse events and asymptomatic illnesses that may impact study results. Vitals will be collected at baseline, 7 hours post-Shoden administration, and at the end of each baseline visit. At the beginning of each baseline visit, participants will complete an electrocardiogram (ECG) and the Geriatric Depression Scale-15. Four teaspoons of blood (20 ml) will be collected for safety labs (CBC, CMP, urinalysis, TSH, serum total testosterone). ECG will be repeated 7 hours post-intervention to assess for cardiac changes. One teaspoon (5 ml) will be collected for a repeat CMP at 10 hours post-intervention to evaluate kidney and liver function. Participants will be interviewed and administered a standardized multi-system adverse events questionnaire at the beginning and end of each baseline visit. This visit is expected to take 13 hours a total of 175 mL of blood will be collected.

If the baseline CBC shows hemoglobin or hematocrit levels below what is recommended by the FDA for blood donation, the visit will be halted immediately. Participants will be asked to stay for 2.5 hours after the study agent has been administered to assess for acute side effects. Two and a half hours was chosen because common withanolides have reached their C_{MAX} by this time based on a previous PK study using Shoden®.⁸⁰ The end-of-visit adverse events questionnaire will be administered by phone and missed safety evaluations (7-hour ECG and vitals, 10-hour CMP, 12-hour vitals) will be collected at the 24-hour visit. After the 24-hour visit, the participant will be withdrawn from the study.

If study staff have difficulties collecting blood samples for any reason, the decision may be made to halt the visit. Participants will be asked to stay for 2.5 hours after the study agent has been administered to assess for acute side effects. If the visit ends before the 7-hour mark, the end-of-visit adverse events questionnaire will be administered by phone and missed safety evaluations (7-hour ECG and vitals, 10-hour CMP, 12-hour vitals) will be collected at the 24-hour visit. Participants will be allowed to remain on the study if difficulties with blood sample collection were the only reason for halting the study visit early.

I.4.2 24- and 48-Hour Visits

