1.6. Four-Week Follow-Up Visit

Participants will be asked to fast for 10-12 hours, excluding water, the night before each four-week follow-up visit in order to collect fasting glucose as part of the CMP. A single blood sample (two teaspoons (10 ml)) and a urine sample will be collected to assess steady state plasma levels and excretion of WS compounds. Returned capsules will be counted to assess for adherence. Participants will have an ECG and blood and urine samples will be sent for safety labs (CBC, CMP, urinalysis, TSH, serum total testosterone, serum DHEA-S). The Geriatric Depression Scale-15 will be administered. At the four-week follow-up visit for the second study period, participants and investigators will be queried as to their perception of the dose sequence administered. This visit is expected to take 45-60 minutes.

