1.8. REDCap Surveys

Participants will be emailed a link to electronic surveys in REDCap at four time points during the study: during the week prior to each PK visit and during the week prior to each four-week follow-up visit. Participants will complete two surveys at each time point: Pittsburgh Sleep Quality Index (PSQI) and the Perceived Stress Scale (PSS).

I.9. Washout Period

The two study periods will be separated by a 2- to 4-week washout period where the participant will not take the study agent. If the washout period is longer than 21 days, participants will be called at two weeks to assess for delayed side effects.

I.10. Subject participation duration

Including the screening visit, a two to four-week washout period between doses, and an exit phone interview for adverse event monitoring, it will take participants 13 to 14 weeks to complete the study.

Table 1. Schedule of study visits and assessments.

	Screen	PK visit			2-week f/u	4-week f/u	Washout Period	PK visit			2-week f/u	4-week f/u	Final visit +2 weeks
Study Period		1			1	1		2			2	2	
Event	Clinic Visit	0 to 12h	24h	48h	Phone visit	Clinic visit		0 to 12h	24h	48h	Phone visit	Clinic visit	Phone visit
Informed consent	X												
Vitals and biometrics	X	X ⁺	X	X		X		X ⁺	X	X		X	
Health screening	X												
Electrocardiogram (ECG)	X	X [§]	X [°]			X		X [§]	X [°]			X	
CBC*, CMP*, TSH [^] , and UA*	X	X [^]	X [°]			X		X [^]	X [°]			X	
Serum testosterone		X				X		X				X	
Single dose of intervention		X						X					
Single-dose PK blood draws		X	X	X				X	X	X			
Issue 35-day supply of Shoden®				X [#]						X [#]			
Steady state PK blood draw						X						X	
12-hour urine collection		X						X					
Single urine collection		X [¶]	X	X		X		X [¶]	X	X		X	
Collect and count unused capsules						X						X	
Adverse events questionnaire		X [*]		X	X	X		X [*]		X	X	X	X
Cognitive screen (MMSE)	X												
Depression screen (GDS)	X	X [♦]			X	X		X			X	X	X
REDCap surveys		X [▼]				X [▼]		X [▼]				X [▼]	

f/u – follow-up

§ ECG collected prior to Shoden® administration and at 7 hours post-Shoden® administration

* CBC = Complete Blood Count with differential; CMP = Comprehensive Metabolic Panel; UA = Urinalysis

^ CMP collected prior to Shoden® administration and at 10-hours post-Shoden® administration

▲ TSH = Thyroid-stimulating hormone

This will take place at the 24-hour visit if 48-hour visit is eliminated, as described in Section I.4.

¶ Aliquot of baseline urine prior to administration of Shoden®

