Peak area for each withanolide analyte and internal standard will be obtained using Analyst software from Sciex Technologies (version 1.7.1). The Core lab will provide and set up LC-MRM-MS instrumentation. The applicant will prepare the plasma and urine samples for analysis in [name] lab and retrieve and analyze the LC-MRM-MS data generated at the Core Lab to obtain concentrations of each withanolide in each sample. The applicant will work with [name] to obtain PK curves and parameters.

L.2. Safety analysis (Aim 2)

Changes in laboratory outcomes from the baseline visit to the four-week follow-up visit for each study period will be presented using descriptive statistics (e.g., means and standard deviations, frequency and percent). Within group differences for laboratory outcomes at each dose will be evaluated for significance using paired t tests. Data will also be presented visually using histograms and line graphs. Treatment-emergent AEs will be organized by body system and summarized in table format by dose, with AE severity and possible relation to study drug reported.

L.3. Feasibility analysis (Aim 3)

The feasibility of administering REDCap surveys will be assessed by calculating the percentage of administered questionnaires that are returned and fully completed by participants, with feasibility defined as at least 80% of all administered questionnaires returned and completed. For each of the four timepoints (prior to PK Visit 1 and 2, prior to 4-Week Follow-Up Visit 1 and 2), the percentage of administered questionnaires returned and the percentage of returned questionnaires that are fully completed will also be reported.

L.4. Sample size

Based on a paired sample t-test with $\alpha=0.05$ and a sample size of 10 (anticipating two dropouts), we will have 95% power to detect an effect size of 1.3 (Cohen's d). Based on plasma levels of withaferin A, withanoside IV, and withanolide A observed in an unpublished PK study of 480 mg Shoden® in 16 healthy adults,⁷⁹ this effect size would be a difference in C_{\max} between the two doses of about 6.5 ng/ml for withaferin A, 2.2 ng/ml for withanoside IV, and 1.17 ng/ml for withanolide A. We expect to see much bigger differences between the two doses based on previous botanical studies where half doses resulted in C_{\max} values that were 35-50% lower than the full dose.⁸¹⁻⁸⁴

L.5. Data quality and management

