- Controlled User Access: REDCap employs a robust multi-level security system that enables researchers to easily implement "minimum necessary" data access for their research staff, including specification of data fields that are identifiers. This feature includes "single click" ability to provide completely deidentified (removing all identified data fields and shifting dates) for analysis or other purposes. User activities are logged to enable auditing of all data access. Access is integrated with OHSU's network such that users who are also OHSU employees are authenticated against their OHSU network credentials.
- Data Integrity: REDCap is jointly managed in accordance with OHSU Information Security Directives by ACC staff and members of OCTRI's Biomedical Informatics Program, ensuring fidelity of database configuration and back-ups. User activities are logged to enable auditing of all data changes.

N. PROVISIONS TO MONITOR THE DATA TO ENSURE THE SAFETY OF SUBJECTS

To ensure participant safety, we will monitor for adverse events (AE) with AE questionnaires, ECGs, and laboratory tests. During the baseline visit and four-week follow-up visit for each study period, participants will undergo an ECG and laboratory testing (CBC, CMP, TSH, testosterone, and urinalysis). At baseline visits, ECG will be repeated 7 hours post-Shoden® administration to assess for cardiac changes and CMP will be repeated 10 hours post-Shoden® administration to evaluate liver and kidney function. Participants whose ECGs and/or lab results reflect abnormalities will be further screened for potential causes of the abnormalities as determined by [name]. We will notify the participant and the participants' primary care physician if blood and urine safety parameters fall outside the normal range or if abnormalities are seen on ECG, and [name] will undertake the necessary steps to ensure appropriate clinical care.

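### DHEA-S is listed only at the four-week visit, so its planned change from baseline cannot be computed; testosterone change has no planned summary by sex

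*Combined protocol and SAP*

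**What the plan says.** Section I.6 (four-week follow-up visit) gives the laboratory list as "safety labs (CBC, CMP, urinalysis, TSH, serum total testosterone, serum DHEA-S". This is the only place where DHEA-S appears as a study measurement. The other lists read as follows.

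- Section I.3 (screening): besides a blood count, "comprehensive metabolic panel (CMP), thyroid-stimulating hormone (TSH), and urinalysis) will be performed". No hormone other than TSH is named.
- Section I.4.1 (baseline visit of each period): "Four teaspoons of blood (20 ml) will be collected for safety labs (CBC, CMP, urinalysis, TSH, serum total testosterone". The list ends there.
- Figure 3 legend: "Safety assessment at study visits includes safety labs (CBC, CMP, TSH, testosterone, UA".
- Section N, covering both the baseline and the four-week visits: "participants will undergo an ECG and laboratory testing (CBC, CMP, TSH, testosterone, and urinalysis".
- Table 1: a row for "Serum testosterone", marked at both PK visits and both four-week visits, and no row for DHEA-S.

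Section L.2 presents laboratory outcomes as change from the baseline visit to the four-week visit of each period and adds: "Within group differences for laboratory outcomes at each dose will be evaluated for significance using paired t tests". It mentions no breakdown by sex. Section F.2.1 plans 6 women and 6 men, and Section H.1 stratifies randomisation by sex.

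On the evidence, Section C.2.3 states: "Several studies have reported increased testosterone levels in males taking WS", and says that this was not seen in females. It also gives rises of 11% and 14.7% in men in two trials of this product.

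**The concern.** A paired change needs two values. For DHEA-S the plan schedules at most the second, so the L.2 analysis has nothing to work on. Section C.2.3 raises DHEA-S as a hormone on which the extract's effect is of unclear safety relevance. A four-week value alone cannot say whether it moved. The background does not help a reader interpret a single level either: Section C.2.3 cites one trial for a decrease in DHEA-S, and Section E.1 cites the same trial for an increase.

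Testosterone raises a different and milder issue. Both values exist, but a single within-dose test over all participants mixes a sex in which the cited trials saw a rise with one in which they did not. The rise in men is also the protocol's stated reason for avoiding the extract after prostate cancer, so it is the result a reader will look for. In a mixed average it would be harder to see.

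**Working it through.** **DHEA-S: which pairs can be formed.**

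| Source | Baseline visit | Four-week visit |
|---|---|---|
| I.4.1 | not listed | – |
| I.6 | – | listed |
| Figure 3 legend | not listed | not listed |
| Table 1 | no row | no row |
| Section N | not listed | not listed |

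The screening labs (I.3) offer no substitute for the first period. Participant-periods: 12 × 2 = 24. With a baseline DHEA-S: 0. Computable changes: 0 of 24, or 0 of 20 with the 10 completers that F.2.1 expects.

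**Testosterone: size of the pooled effect.** Inputs: +11% and +14.7% in men (C.2.3), equal numbers per sex (F.2.1), and an assumed zero change in women. Averaging individual percent changes:

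- (6 × 11% + 6 × 0%) / 12 = 5.5%
- (6 × 14.7% + 6 × 0%) / 12 = 7.35%, about 7.4%

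L.2 does not name a scale. On raw values, the pooled change relative to the pooled baseline is the male percentage divided by (1 + r), where r is the ratio of women's to men's mean level. The documents do not give r. For an 11% rise, r = 0.05 gives 11 / 1.05 = 10.5%, and r = 1 gives 11 / 2 = 5.5%. The halving therefore belongs to the equally weighted percent scale.

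**Testosterone: power.** The plan's only power figure, in L.4, concerns the C_max comparison: 95% for d = 1.3 with n = 10, two-sided 0.05. The noncentral t with 9 degrees of freedom and noncentrality 1.3 × √10 = 4.11 gives 95.4%, so that figure reproduces. No power is stated for the laboratory tests.

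For a rise of d (in units of the SD of change in men) in men only, with women's SD equal to s times men's and equal numbers, the pooled standardised effect is

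(d/2) / √[(1 + s²)/2 + d²/4].

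At d = 1.3:

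- s = 1: 0.65 / √(1 + 0.4225) = 0.545
- s near 0: 0.65 / √(0.5 + 0.4225) = 0.677

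Pooling halves the numerator, and the difference between the sexes adds to the SD. Simulated power of the two-sided paired t-test (100,000 runs; s = 1 and s = 0.05) is:

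| d in men | 5+5 pooled, s = 1 | 5+5 pooled, s = 0.05 | 5 men alone | 6+6 pooled, s = 1 | 6+6 pooled, s = 0.05 | 6 men alone |
|---|---|---|---|---|---|---|
| 0.5 | 10% | 9% | 14% | 11% | 14% | 17% |
| 1.0 | 22% | 30% | 40% | 27% | 44% | 51% |
| 1.3 | 30% | 47% | 59% | 38% | 66% | 72% |
| 2.0 | 48% | 83% | 91% | 61% | 95% | 97% |

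Men alone do better throughout, despite half the sample. They are still too few for a dependable test: 80% power needs d = 1.68 with 5 men or d = 1.43 with 6. The documents give no SD for testosterone change, so 11–14.7% cannot be converted to d, and d is shown as a range. The 5 + 5 split assumes that the two expected dropouts fall one in each sex.

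**The case against.** **DHEA-S may be a stray entry.** It appears in one list, and three other places omit it at the very visit where I.6 includes it. Section C.2.3 discusses the hormone and then commits only to measuring testosterone. This stands: the documents do not show whether a DHEA-S analysis was intended. The lists must be reconciled, and deletion is a legitimate outcome.

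**The four-week values are not useless.** In a crossover, each participant who completes both periods would have one value per dose, which allows a within-person comparison of 240 and 480 mg. That is correct, but L.2 does not plan it. With no placebo and no baseline, it would not show change from untreated levels.

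**A baseline might be recovered later.** Pre-dose plasma is drawn (I.4.1) and specimens are stored (K.4). No such assay is planned, though, and I.6 specifies serum.

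**On testosterone, a reader might infer three stronger claims that the documents do not support.**

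- That the whole hormone analysis fails. It does not: testosterone is measured at the start and end of both periods, and the paired test can be run.
- That the protocol expects an effect in men only. The sex difference is cited background. Aim 2's hypothesis concerns tolerability and severe adverse events.
- That pooling is prescribed. L.2 is silent on sex; pooling is simply its plain reading.

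**Unadjusted tests.** A reader might also count many unadjusted laboratory tests and predict a number of chance findings. The documents do not say how many parameters will be tested, so no such count is supported.

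**The conflict on direction.** The opposite DHEA-S directions attributed to one trial are a background inconsistency that should be corrected against the source. A two-sided test does not depend on it.

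**Scale.** Safety is a secondary endpoint in a 12-person pilot sized on C_max. Even the men-only analysis has limited power, so a split by sex is good descriptive reporting rather than the repair of a broken test.

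**Conclusion.** The DHEA-S point holds on the text alone and needs no assumption. As listed, the change that L.2 analyses cannot be computed for DHEA-S in either period, and I.6 disagrees with the Figure 3 legend, Table 1 and Section N about whether it is measured at all.

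The testosterone point holds in a limited form. The planned test can be run, but L.2 provides no view by sex where the cited evidence differs by sex. The size depends on assumptions: no change in women, equal numbers, and a percent scale for the halving to about 5.5–7.4%; an assumed men-only d = 1.3 and 5 + 5 completers for power of 30–47% pooled against 59% in men alone. Both points are worth correcting because they are cheap. Neither affects the primary PK analysis.

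**What to change.** **DHEA-S: choose one and make every list agree.**

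- If it is wanted: add it to the pre-dose safety draw at both baseline visits (I.4.1), and to the Figure 3 legend, Table 1 and Section N for both baseline and four-week visits. Cost: at most 12 × 2 = 24 added assays. If the laboratory confirms that the existing 20 ml is enough, the baseline-visit blood total does not change (20 + 15 × 10 + 5 = 175 ml). Pre-dose values not collected at the visit may not be recoverable, so the change should come before further baseline visits.
- If it is not intended: delete it from I.6, at no cost.

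**Testosterone (and DHEA-S if kept): add a sentence to L.2.** For each dose, summarise the log or percent change from the same period's baseline separately for men and women, with a 95% confidence interval, as a descriptive analysis and not as a powered test. The data are already collected and sex is already a randomisation stratum, so for testosterone the cost is wording only. The downside is wide intervals at 5 to 6 participants per sex, which the report should say plainly.
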